10.2.4. Demographic and baseline characteristics

The following analysis will be performed on the Randomized set.

The participants' demographic characteristics and baseline characteristics will be summarized by sequence and overall and listed.

Tables by sequence and overall with the number of participants having at least one medical or surgical history and a corresponding listing will be prepared.

Tables by sequence and overall with number of participants having at least one previous treatment will be prepared. The same table will be prepared for concomitant treatments.

Details of drug dosing and meals will be listed.

10.2.5. Protocol deviations

A summary table of important protocol deviations by sequence and overall and the corresponding listing will be prepared.

10.2.6. Pharmacokinetic analysis

The analysis will be performed on the Pharmacokinetic Set.

Relevant PK parameters will be calculated for binimatinib and AR00426032 (see Section 9.3.4) by standard non-compartmental methods for those participants with sufficient plasma concentration data.

Plasma concentration and PK parameters

Plasma concentrations (binimatinib and AR00426032) will be summarized over time by formulation and corresponding listings will be prepared.

Concentration-time profile plots will be prepared on linear and log-linear coordinates for each participant with both formulations on the same graph, as well as arithmetic mean (\pm SD) with both formulations on the same graph.

Binimatinib and AR00426032 PK parameters will be summarized by formulation and corresponding listings will be prepared.

For binimatinib only:

- Scatter plots and box whisker plots will be generated for the comparison of C_{max} , AUC_{last} and AUC_{inf} .
- To demonstrate the bioequivalence between the two formulations, primary PK parameters (AUC_{last} , AUC_{inf} and C_{max}) will be analyzed separately using linear mixed effects model with log-transformed PK parameter as the dependent variable, sequence, period and formulation as fixed effects and participant with sequence as random effect. Point estimates and 90% CIs will be provided for the ratio of Test to Reference (3 x 15 mg formulation as Reference and 45 mg formulation as Test). Bioequivalence will be declared if the 90% CI for the ratio of Test to Reference geometric means is within the range of 0.80 to 1.25 for all primary endpoints.
- T_{max} will be analyzed using non-parametric tests.

10.2.7. Safety analysis

10.2.7.1. Criteria

- AEs.
- Vital signs/temperature.
- Standard 12-lead ECG.
- Hematology, blood chemistry, coagulation, urinalysis.
- Complete physical examination, weight.
- Visual examination.
- Ophthalmologic examination.
- COVID-19 tests.

10.2.7.2. Statistical methodology

Descriptive analysis of safety parameters will be performed on the Safety set.

AEs will be considered treatment-emergent if they start or worsen during the on-treatment period.

TEAEs will be summarized by system organ class and preferred term in tables with:

- The number of participants with at least one TEAE and the number of TEAEs for each formulation.

Analyses taking into account severity and drug relationship to treatment will be also carried out. All AEs will be listed.

The description will be performed by formulation and measurement time (when applicable) for measurements during the two treatment periods, and overall for measurements performed at screening and EOS visits.

For vital signs and ECG parameters, potentially clinically significant abnormalities (PCSA) will be specified in the SAP and participants with PCSA values will be summarized.

The presence of orthostatic hypotension and abnormal HR increase will be derived and the number and percentage of participants with at least one orthostatic hypotension/ abnormal HR increase will be presented by formulation and measurement time, as well as a corresponding listing.

Visual and ophthalmologic abnormalities and dermatological abnormalities will be described, and corresponding listings will be generated.

Laboratory data (hematology, biochemistry, coagulation and urinalysis) will be described. For laboratory tests covered by the NCI-CTCAE (version 5.0 [16]), laboratory data will be graded accordingly, Grade 0 will be assigned for all non-missing values not graded as 1 or higher. Grade 5 (death) will not be used.

For laboratory tests where grades are not defined by NCI-CTCAE, results will be graded by the low/normal/high classifications based on laboratory normal ranges.

All laboratory parameters will be listed.

12. APPENDICES

Appendix 1: Regulatory and legal considerations

RIGHT OF ACCESS TO DATA AND SOURCE DOCUMENTS

Monitoring

The Investigator will allow the representative of the Sponsor and the study Monitor:

- To check and to verify the site, the facilities and the material used for the study.
- To meet all members of the team involved in the study.
- To consult all the documents relevant to the study.
- To check that the eCRFs have been correctly completed.
- To have direct access to source documents for comparison of data therein with the data in the eCRFs.
- To check that AEs have been documented.
- To verify that the study is carried out in compliance with the protocol.

This study will be monitored at regular intervals, by mutual agreement of the Investigator and Monitor.

All information dealt with during these visits will be treated as strictly confidential.

The Investigator will provide the Sponsor with the following:

- Study status updates at regular intervals.
- Adequately completed eCRFs.

Audit - Inspection

The Investigator will be informed that an audit will be carried out, at the request of the Sponsor, before, during or after the study.

The Investigator will be informed that the Regulatory Authorities may also carry out an inspection. In this case, the Investigator must inform the Sponsor as soon as he receives the notification of inspection.

The Investigator must allow the representatives of the Regulatory Authorities and persons responsible for the audit to:

- Inspect the site, facilities and material used for the study.
- Meet all members of his team involved in the study.
- Have direct access to study data and source documents.
- Consult all the documents relevant to the study.

QUALITY CONTROL AND QUALITY ASSURANCE

Written procedures describing data flow, data entry or electronic capture, data cleaning and processing, and required quality control must be utilized.

Trained site personnel must conduct data entry, or data must be transferred electronically from the device into the EDC system.

The entered/electronically transferred data will be systematically checked by the clinical research organization (Biotrial) staff, either by using error messages printed from validation programs or by manual checks carried out based on database listings. Data checks for data consistency and plausibility must be defined and implemented in the EDC system. Queries are raised and resolved electronically within the EDC system.

After the completion of the data cleaning and data review process and full resolution of the data queries, the database will be locked. Any changes to the database after that time may only be made by joint written agreement between the Sponsor and the Investigator.

The Investigator must guarantee the confidentiality of the study data in the medical files by implementing security measures to prevent unauthorized access to the data and to the computer system.

STUDY SUSPENSION, TERMINATION, AND COMPLETION

The Sponsor may suspend or terminate the study or any part of the study at any time for any reason.

If the Investigator suspends or terminates the study, the Investigator will promptly inform the Sponsor and the regulatory authorities and provide them with a detailed written explanation. The Investigator will also return all test articles, test article containers, and other study materials to the Sponsor.

Upon study completion, the Investigator will provide the Sponsor and IEC with final reports and summaries as required by regulations.

ETHICS AND REGULATORY ASPECTS

Current texts

The study will be carried out in accordance with:

- The most recent recommendations of the World Medical Association (WMA).
- The International Council on Harmonization (ICH) recommendations: Good Clinical Practice (GCP) [E6 (R2)], (CPMP/ICH/135/95), 2016.
- Decree of 26th April 2006 (n°2006-477) relative to biomedical research and French law n°2002-303 of 4th March 2002 regarding participant's rights.
- French law n°78-17 of 6th January 1978 relative to Data processing, Data files and individual liberties, modified by law n°2016-41 of 26 JAN 2016, ruling n°2016-800 of 16 JUN 2016 and updated by deliberation n°2016-262.
- European directive 2005/28/CE dated 8 April 2005 (GCP) translated in French law by the Decision of 24 Nov 2006 setting the GCP for biomedical research on drugs for human use.
- Regulation (EU) 2016/679 of the European Parliament and of the Council of 27 April 2016 on the protection of natural persons with regard to the processing of personal data and on the free movement of such data.
- Guidance for Industry; Handling and Retention of BA and BE samples; U.S. Department of Health and Human Services; Food and Drug Administration Center for Drug Evaluation and Research (CDER); May 2004.

Participant Information and Consent

An unconditional prerequisite for a participant's participation in the trial is his/her written informed consent. The volunteer's written informed consent to participate in the trial must be given before any trial-related activities are carried out. Nevertheless, if necessary and after agreement of the Sponsor, any measures identical to those planned in the protocol for the participants' screening that have already been performed within the timelines given by the protocol for the screening exams could be used for the protocol in order to minimize the constraints on the participants.

Participants will be verbally informed by an Investigator of all pertinent aspects of the trial: the nature of the study, its aim, its possible risks and restrictions, its duration and the fee that they will receive. The protocol will be explained during a meeting prior to the study and each participant must be informed that participation in the study is voluntary and that he/she may withdraw from the study at any time. At this meeting, an information sheet will be given to each participant. The language used in doing so must be chosen so that the information can be fully and readily understood by lay persons.

The participant should carefully read before signing and dating the informed consent form. He/She can ask all necessary questions to the Investigator. After having obtained answers to his/her satisfaction and being given sufficient time to think about their decision (up to a few days), the participant can then decide whether or not to take part in the study. The informed consent form must be signed and personally dated by both the participant and the Investigator. A copy of the signed document should be given to the participant.

On request by the Sponsor, a copy of the signed information sheets and informed consent forms will be retained in a sealed envelope by the Investigator and delivered to the Sponsor at the end of the study for archiving. Under no circumstances will this envelope be opened by the Sponsor.

It may only be examined at the request of Regulatory Authorities. A copy will be kept by the Investigator for 25 years or according to the Sponsor's procedures, whichever is longer (the third copy is given to the participant).

The completed "participant screen log" will be signed by the Investigator to attest that consent has been obtained from all participants.

Whenever important new information becomes available that may be relevant to the participant's consent, the written participant information sheet and any other written information provided to participants will be revised by the Sponsor and be submitted again to the IEC for review and favorable opinion/authorization. The agreed, revised information will be provided to each participant in the trial for signing and dating. The Investigator will explain the changes from the previous version.

Submission to the authorities

Ethics Committee (CPP)

It is the responsibility of the Sponsor to seek and obtain the favorable opinion of the CPP (Comité de Protection des Personnes, i.e., Independent Ethics Committee). This activity is delegated to Biotrial.

The present clinical trial will not be initiated until this favorable opinion is obtained.

ANSM authorization

It is the responsibility of the Sponsor to seek and obtain the ANSM (French Drug Agency) authorization for conducting the present clinical trial. This activity can be delegated to Biotrial.

The present clinical trial will not be initiated until the ANSM authorization is received.

Protocol Amendments

Any significant change (substantial modification) in the study requires a protocol amendment for authorization or for information. Concerning a protocol amendment sent to ANSM and/or IEC for authorization, an Investigator must not make any changes to the study without regulatory authorities and Sponsor approval except when necessary to eliminate apparent immediate hazards to the participants. A protocol change intended to eliminate an apparent immediate hazard to participants may be implemented immediately, but the change must then be documented in an amendment, reported to the regulatory authorities/IEC within 5 working days, and submitted in the required time frame. All protocol amendments must be reviewed and approved following the same process as the original protocol.

Regulatory requirements

In compliance with French law, approval as a site for clinical research without direct individual therapeutic benefit was granted to [name] by the Minister for Health to Biotrial Rennes center (site n°05001M).

DATA PROCESSING AND ARCHIVING OF DOCUMENTS AND DATA RELATIVE TO THE RESARCH

After the study, the Investigator will keep all information relevant to the study for 25 years, or according to the Sponsor's procedures, whichever is longer.

CONFIDENTIALITY AND AGREEMENTS

Confidentiality

Before starting the study, the Investigator must confirm receipt of adequate documentation from the Sponsor so as to be able to decide whether or not to perform the study.

All documents and information given to the Investigator by the Sponsor with respect to the study are strictly confidential.

The Investigator and his colleagues agree to use them only with the framework of this study, in order to carry out the protocol. This agreement is binding as long as the confidential information has not been disclosed to the public by the Sponsor.

The Investigator may use the technical protocol to obtain the informed consent of study participants. It must not be disclosed to other parties without the written authorization of the Sponsor.

The Investigator keeps a confidential participant identification list for the study. The Investigator must maintain source documents for each participant in the study.

Data on participants collected in eCRFs during the study will be documented in an anonymous fashion. All information in the eCRFs must be traceable to these source documents.

REPORT AND PUBLICATION

Report:

The results of the study will be reported in a Clinical Study Report. This report will be prepared by Biotrial according to existing Standard Operating Procedures (ICH Biotrial or Sponsor own format).

In compliance with the regulations, the final report will be produced within one year of completing the study and in agreement with the work order.

The final report will be provided to all Investigators having included participants in the study.

The clinical study report will be provided as Word and PDF files. Also, SAS transfer files of the data will be provided electronically. All data will be presented CTD-compliant.

Publication:

The Investigator will only use the information in the context of the study. The information cannot be used without the Sponsor's authorization. Hence, all or part of the information should only be divulged, submitted for publication or claimed for industrial proprietary act with the written consent of the Sponsor.

Appendix 2: Adverse event and serious adverse event definitions

Definitions

AE Definition

- An AE is any untoward medical occurrence from signature of informed consent in a patient or clinical study participant, temporally associated with the use of study intervention, whether or not considered related to the study treatment.
- NOTE: An AE can therefore be any unfavorable and unintended sign (including an abnormal laboratory finding), symptom, or disease (new or exacerbated) temporally associated with the use of study treatment.

Events Meeting the AE Definition

- Any abnormal laboratory test results (e.g., hematology, clinical chemistry, or urinalysis) or other safety assessments (e.g., ECG, radiological scans, vital signs measurements), including those that worsen from informed consent signature, considered clinically significant in the medical and scientific judgment of the Investigator (i.e., not related to progression of underlying disease).
- Any new or worsening of the AE that is assessed by the Investigator as related to the disease progression must be reported as an AE.
- Exacerbation of a chronic or intermittent pre-existing condition including either an increase in frequency and/or severity of the condition.
- New conditions detected or diagnosed after informed consent signature even though it may have been present before the start of the study.
- Signs, symptoms, or the clinical sequelae of a suspected drug-drug interaction.
- Signs, symptoms, or the clinical sequelae of a suspected overdose of either study intervention or a concomitant medication. The event of an overdose itself meets the definition of an Adverse Event and should be reported as an AE/SAE.

Events NOT Meeting the AE Definition

- Medical or surgical procedure (e.g., endoscopy, appendectomy): the condition that leads to the procedure is the AE.
- Situations in which an untoward medical occurrence did not occur (social and/or convenience admission to a hospital).

• Adverse Drug Reactions

An adverse drug reaction (ADR) is a response to a medicinal product which is noxious and unintended. A causal relationship between a medicinal product and an AE is at least a reasonable possibility. An adverse reaction, in contrast to an AE, is characterized by the fact that a causal relationship between a medicinal product and an occurrence is suspected.

Serious Adverse Events or Serious Adverse Drug Reactions

If an event is not an AE per definition above, then it cannot be an SAE even if serious conditions are met.

A SAE is defined as any untoward medical occurrence that, at any dose:

a. Results in death

b. Is life-threatening

The term 'life-threatening' in the definition of 'serious' refers to an event in which the participant was at risk of death at the time of the event. It does not refer to an event, which hypothetically might have caused death, if it were more severe.

• Requires inpatient hospitalization or prolongation of existing hospitalization

- In general, hospitalization signifies that the participant has been detained (usually involving at least an overnight stay) at the hospital or emergency ward for observation and/or treatment that would not have been appropriate in the physician's office or outpatient setting. Complications that occur during hospitalization are AEs. If a complication prolongs hospitalization or fulfils any other serious criteria, the event is serious. When in doubt as to whether "hospitalization" occurred or was necessary, the AE should be considered serious.
- Hospitalization for elective treatment of a pre-existing condition that did not worsen from baseline is not considered an AE.

Any hospitalization, or prolongation of hospitalization due to the circumstances listed below will not be notified as a SAE to the Sponsor by the Investigator:

- planned (as per protocol) medical/surgical procedure including 24 hours hospitalization after the first treatment administration,
- preparation for routine health assessment/procedure (e.g., routine colonoscopy),
- planned medical/surgical admission (planned prior to entry into study trial, appropriate documentation required),
- administrative or social reasons (e.g., lack of housing, economic inadequacy, care-giver respite, family circumstances)

c. Results in persistent disability/incapacity

- The term disability means a substantial disruption of a person's ability to conduct normal life functions.
- This definition is not intended to include experiences of relatively minor medical significance such as uncomplicated headache, nausea, vomiting, diarrhea, influenza, and accidental trauma (e.g., sprained ankle) which may interfere with or prevent everyday life functions but do not constitute a substantial disruption.

d. Is a congenital anomaly/birth defect

e. Other situations:

- Medical or scientific judgment should be exercised in deciding whether SAE reporting is appropriate in other situations such as important medical events that may not be immediately life-threatening or result in death or hospitalization but may jeopardize the participant or may require medical or surgical intervention to prevent one of the other outcomes listed in the above definition. These events should usually be considered serious.
- Examples of such events include invasive or malignant cancers, intensive treatment in an emergency room or at home for allergic bronchospasm, blood dyscrasias or convulsions that do not result in hospitalization, or development of drug dependency or drug abuse.

Suspected Unexpected Serious Adverse Reaction

A SUSAR is an unexpected SAE having a reasonable possibility of a causal relationship with the study drug.

New Safety Medical Fact

According to:

- French law n°2012-300 of 12 MAR 2015 and decree n°2016-1537 of 16 NOV 2016 (modified by decree n°2017-884 of 09 MAY 2017) relative to research on human persons, articles R1123-46 to R1123-62.

A new safety medical fact is any new safety data which could lead to a new evaluation of the benefit/risk balance of the research or the study treatment or which could be sufficient to consider changes to the administration of the study treatment, the conduct of the research, the documents relating to the research, or to stop or amend the protocol or similar studies. Biotrial and the Sponsor will follow the instructions for ensuring the safety of the participants and for the submission/reporting of the new safety medical fact to the French health authorities that are defined in the Safety Management Plan.

Other Reportable Information: Certain information, although not considered an SAE, must be recorded, reported, and followed up as indicated for an SAE. This includes:

- Overdose of an investigational product as specified in this protocol (see Section 9.4.6) with or without an AE.
- Medication errors and uses outside what is foreseen in the protocol, including misuse and abuse of the product, with or without an AE.

Medication Error, Misuse and Abuse

Medication error refers to an unintentional error in dispensing or administration of the study treatment not in accordance with the protocol.

Misuse is defined as any situation where the study treatment is intentionally and inappropriately used not in accordance with the protocol.

Abuse is defined as the persistent or sporadic intentional excessive use of the study treatment, which is accompanied by harmful physical or psychological effects.

Causal relationship with trial medication

The relationship of an AE to the investigational product is a clinical decision by the Investigator based on all available information at the time of the completion of the eCRF and is graded as follows:

1. **No reasonable possibility:** a reaction for which sufficient information exists to indicate that the etiology is unrelated to the study treatment; the participant did not receive the study medication or the temporal sequence of the AE onset relative to administration of the study medication is not reasonable or the event is clearly related to other factors such as the participant's clinical state, therapeutic intervention or concomitant therapy.
2. **Reasonable possibility:** a reaction that follows a reasonable temporal sequence from administration of the drug or in which the drug level has been established in body fluids or tissues, that follows a known or expected response pattern to the suspected drug, and that is confirmed by improvement on stopping or reducing the dosage of the drug, and reappearance of the reaction on repeated exposure (re-challenge).

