9.4.2. Method of Detecting, Recording and Reporting AEs and SAEs

The Investigator and any qualified designees are responsible for detecting, documenting, and recording events that meet the definition of an AE or SAE and remain responsible for following up AEs that are serious, whatever the relationship to the study treatment or study procedures, or that caused the participant to discontinue the study treatment.

Care will be taken not to introduce bias when detecting AEs and/or SAEs. Open-ended (participant's spontaneous reporting) and non-leading verbal questioning of the participant is the preferred method to inquire about AE occurrences.

The methods of recording, evaluating, and assessing causality of AE and SAE are the following.

AE and SAE Recording

- When an AE/SAE occurs, it is the responsibility of the Investigator to review all documentation (e.g., hospital progress notes, laboratory reports, and diagnostics reports) related to the event.
- For a recurrent AE that resolves and subsequently recurs, each recurrence must be recorded as a separate AE.
- For a continuous AE (i.e., unresolved between participant assessments), any change in severity (improvement or worsening) or seriousness must be recorded with the indication of the start and (if applicable) the end of the change within the same AE eCRF form.
- The Investigator will then record all relevant AE/SAE information in the eCRF.
- It is **not** acceptable for the Investigator to send photocopies of the participant's medical records to Sponsor in lieu of completion of the AE/SAE eCRF page/SAE form.
- There may be instances when copies of medical records for certain cases are requested by the Sponsor. In this case, all participant identifiers, with the exception of the participant number, will be redacted on the copies of the medical records before submission to the Sponsor.
- The Investigator will attempt to establish a diagnosis of the event based on signs, symptoms, and/or other clinical information. Whenever possible, the diagnosis (not the individual signs/symptoms) will be documented as the AE/SAE.

Assessment of Severity

The Investigator will make an assessment of severity for each AE and SAE reported during the study, and grade them using NCI-CTCAE V5.0 [16].

For any term that is not specifically listed in the NCI-CTCAE scale, severity should be assigned a grade of 1 through 5 using the following NCI-CTCAE guidelines:

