- Grade 1: Mild; asymptomatic or mild symptoms; clinical or diagnostic observations only; intervention not indicated.
- Grade 2: Moderate; minimal, local or non-invasive intervention indicated; limiting age-appropriate instrumental activities of daily living.
- Grade 3: Severe or medically significant but not immediately life-threatening; hospitalization or prolongation of hospitalization indicated; disabling; limiting self-care activities of daily living.
- Grade 4: Life-threatening consequences; urgent intervention indicated.
- Grade 5: Death related to AE.

An event is defined as 'serious' when it meets at least 1 of the predefined seriousness criteria as described in the definition of an SAE (see [Appendix 2](#)), NOT when it is rated as severe.

Assessment of Causality

The Investigator is obligated to assess the relationship between study treatment and each occurrence of each AE/SAE.

- A “reasonable possibility” of a relationship conveys that there are facts, evidence, and/or arguments to suggest a causal relationship, rather than a relationship cannot be ruled out.
- The Investigator will use clinical judgment to determine the relationship.
 - Alternative causes, such as underlying disease(s), concomitant therapy, and other risk factors, as well as the temporal relationship of the event to study treatment administration will be considered and investigated.
- The Investigator will also consult the Investigator’s Brochure [1] and/or Product Information [12], for marketed products, in his/her assessment.
- For each AE/SAE, the Investigator **must** document in the medical notes that he/she has reviewed the AE/SAE and has provided an assessment of causality.
- There may be situations in which an SAE has occurred, and the Investigator has minimal information to include in the initial report to Pierre Fabre Corporate Vigilances Division. However, it is very important that the Investigator always make an assessment of causality for every event before the initial transmission of the SAE data to Pierre Fabre Corporate Vigilances Division.
- The Investigator may change his/her opinion of causality in light of follow-up information and send a SAE follow-up report with the updated causality assessment.
- The causality assessment is one of the criteria used when determining regulatory reporting requirements.

Details regarding the grading of the causal relationship of an AE/SAE with study medication are provided in [Appendix 2](#).

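### Appendix 2 makes reappearance on re-challenge a condition of the only positive causality grade, which a first-occurrence event in this two-dose crossover cannot literally meet

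*Protocol*

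**What the plan says.** Protocol 9.4.2 (Assessment of Causality) explains that a reasonable possibility "conveys that there are facts, evidence, and/or arguments to suggest a causal relationship", and adds that merely being unable to exclude a relationship is not the standard. It then hands grading over: "Details regarding the grading of the causal relationship of an AE/SAE with study medication are provided in" Appendix 2. On timing, the investigator must "always make an assessment of causality for every event before the initial transmission of the SAE data", and "The Investigator may change his/her opinion of causality in light of follow-up information". On recording, "For a recurrent AE that resolves and subsequently recurs, each recurrence must be recorded as a separate AE".

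Appendix 2 states that the relationship "is a clinical decision by the Investigator based on all available information at the time of the completion of the eCRF" and gives two grades:

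- **No reasonable possibility:** "a reaction for which sufficient information exists to indicate that the etiology is unrelated to the study treatment". The situations named are that the drug was not received, the timing is not reasonable, or the event clearly has another cause.
- **Reasonable possibility:** a reasonable temporal sequence or an established drug level, a known or expected response pattern, and a reaction "that is confirmed by improvement on stopping or reducing the dosage of the drug, and reappearance of the reaction on repeated exposure (re-challenge".

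The same appendix defines an adverse drug reaction by a suspected relationship, and a SUSAR as an unexpected SAE with a reasonable possibility of a causal link.

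The grade is used in the relatedness-based stopping rules of Protocol 8.2 and in the related-TEAE rows and the by-causality table of SAP 11.1.

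**The concern.** In the positive grade the only alternative offered is between timing and drug level. Everything after that is joined by 'and', and nothing marks the list as illustrative. Read as written, re-challenge is a requirement, in a study where participants are dosed twice and most decisions about relatedness fall before or after the only re-exposure.

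The protocol therefore holds two incompatible meanings of the same phrase, and the unworkable one sits in the text to which investigators are sent for grading. At stake are the count of related TEAEs, part of the secondary safety comparison, and clarity about which collected grade satisfies the relatedness condition in the stopping rules.

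**Working it through.** The plan gives no figure to reproduce. The check is to apply the two grades to the events this design can produce, compare them with the other definitions, and count where the grade is used.

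**1. Logic of the positive grade.** (Timing or drug level) and known or expected pattern and improvement on stopping or reducing and reappearance on re-challenge. With single doses there is no continuing dose to stop or reduce. Resolution during washout could reasonably be read as improvement on stopping, so re-challenge is the binding condition.

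**2. Application to the design.** Two single 45 mg doses at least 7 days apart (Protocol synopsis, 5.1).

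- *Event after dose 1, graded before dose 2.* Re-exposures so far: 0. The positive grade is not met. With plausible timing and no evident other cause, the negative grade is not met either.
- *Event first seen after dose 2.* No further dose is scheduled, so the positive grade can never be met.
- *Event after dose 1 that stops dosing under 8.2.* No re-challenge follows while the stop stands.
- *Event after dose 1 that resolves and recurs after dose 2.* The recurrence is a separate AE and could meet the grade. The first event could be regraded on follow-up, but this is not automatic: SAP 11.1 note iii takes the highest causality only for changes within the same treatment period.

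**3. Comparison with the other definitions.**

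- 9.4.2: facts, evidence or arguments that suggest causation are enough. Contradicted.
- Adverse drug reaction: suspicion is enough. Contradicted.
- SUSAR: the event is unexpected, while the grade asks for a known or expected pattern. This is tension rather than absolute conflict, because a known class effect can still be unexpected in the regulatory sense.

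**4. Use in Protocol 8.2.** There are 7 individual and 3 study-level rules.

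- Individual rules resting on relatedness: serious reaction, severe reaction, undue risk, QTcF, ophthalmologic = 5 of 7. The two ALT/AST rules need no causality.
- Study-level rules resting on relatedness: serious reaction, severe reactions, undue risk = 3 of 3.
- Total 5 + 3 = 8 of 10. Of these, 4 are worded as adverse reactions, so the suspicion-based definition supports them, and 3 are left to the principal investigator's judgement. That leaves 8 − 4 − 3 = 1 with neither anchor: QTcF prolongation qualified as drug-related.
- All 5 individual relatedness rules can change a participant's dosing only between dose 1 and dose 2, when re-exposures number 0. The ophthalmologic rule is explicit: relatedness is judged in order to decide on the second dose.

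**5. Use in SAP 11.1.** 6 of 12 overview rows are restricted to related events, and 1 of 3 TEAE summary tables is by causality. Protocol 7.4 allows no dose modification, so the two dose-reduction rows should be empty, leaving 6 − 1 = 5 of 12 − 2 = 10 informative rows. With 10 or fewer TEAEs, only a listing is produced.

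**The case against.** The strongest defence is that no investigator would apply the text literally. Appendix 2 calls the grade a clinical decision on the information available at eCRF completion, and future re-challenge data cannot be available then. Section 9.4.2 supplies a workable definition, calls for clinical judgement and allows updates. This stands as a reason to call the consequence conditional. It does not rescue the text, because 9.4.2 itself refers grading to Appendix 2, and the plan should not rely on staff setting aside the wording they are sent to.

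Several stronger inferences are tempting, and the documents do not support them:

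- *That the stopping rules fail.* Seven of the 8 relatedness rules have another anchor. The investigator may also withdraw a participant for safety (8.1) and should stop treatment judged detrimental (8.3). Exclusion criteria, including the QTcF limits, are rechecked on Day -1 of Period 2 (Section 2, footnote c). That recheck does not catch every transient QTcF change, but the remaining gap is small.
- *That ungraded events disappear.* Assessment is mandatory for every AE, and SAP section 6 by default shows missing values as a separate category. A rule counting missing grades as related is not needed.
- *That every doubtful event should default to the positive grade.* This is the cannot-be-excluded standard that 9.4.2 rejects. Under 8.2 a single possibly related SAE stops dosing for the whole study, with restart subject to the authorities' agreement.
- *That the pilot shows the standard in use.* One of 14 participants had retinal exudates judged related (3.2.5), but the documents give neither the causality scale used nor whether the event recurred.

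**Conclusion.** The point holds as a wording error in a stated rule. The only positive causality grade cannot literally be met by a first occurrence at the time of grading, and never by an event first seen after dose 2. It contradicts 9.4.2 and the adverse drug reaction definition, and is in tension with the SUSAR definition.

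The size of the effect cannot be derived from the documents, which give no expected number of TEAEs and no evidence of how investigators will read the text. Under-counting of related TEAEs assumes that the text is applied literally and that events fitting neither grade are entered as 'No reasonable possibility'. Within 8.2 the unanchored exposure is 1 rule of 10.

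A reader might infer bias between formulations. None is shown: in the two sequences each formulation is given in both periods, and the same grading text applies to both. The PK primary analysis, the ALT/AST rules and the all-TEAE tables do not use the grade, and in-study SAEs are reported whatever the relationship (9.4.4). The point is worth correcting because the remedy is cheap, not because a distortion has been demonstrated.

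**What to change.** - **Appendix 2:** replace the 'Reasonable possibility' text with the 9.4.2 definition, including its statement that inability to exclude a relationship is not enough. List known or expected pattern, dechallenge and re-challenge as supportive factors, none of them required.
- **Protocol 8.2:** keep the 'at least possibly related' wording, so that the stopping threshold is not raised. Add that any event graded 'Reasonable possibility' meets every relatedness phrase in the section, including drug-related in the QTcF rule.
- **SAP 11.1:** state that a related TEAE is one graded 'Reasonable possibility'.

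The cost is a protocol wording amendment and one SAP line, with no new data, visits or participants. The downside is possibly slightly more events counted as related, and with them possibly more reviews under 8.2.
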